### 9.3.2 Baseline/Day 1 (Visit 1)

Epoetin alfa dosing will have been stopped for a minimum of 5 days in the Main study or 2 days in the ESA hyporesponder parallel study until Baseline/Day 1.

On Baseline/Day 1, blood sample collection and other Baseline/Day 1 procedures will be completed prior to dosing with study drug (vadadustat or epoetin alfa). On Baseline/Day 1, study drug will be administered at the study site, and will be administered after the PK sample is collected and prior to the dialysis session.

At Baseline/Day 1, the following activities/procedures will be performed:

- Review of study eligibility criteria
- Review acceptable methods of contraception
- Abbreviated, symptom-directed physical examination, at the discretion of the Investigator, as clinically indicated
- 12-lead ECG. ECGs will be completed prior to blood draws when possible and will be obtained after the subject has been resting supine comfortably for approximately 5 minutes; ECG may be completed and reviewed by the Investigator on Baseline/Day 1 or if needed for scheduling reasons (e.g., dialysis treatment is scheduled for early morning of Baseline/Day 1), the ECG can be completed and reviewed up to 1-3 days prior to Baseline/Day 1.
- Randomization
- Vital signs including temperature, HR, BP, RR and SO2 (assessed in seated position after 5 minutes of rest and prior to blood draws), and dry weight
- Laboratory Procedures:
  - CBC (including differential)
  - Reticulocyte count
  - CRP
  - Serum chemistry
  - LFTs
  - Iron indices
  - Lipid profile
  - Biomarkers (VEGF, and Hepcidin)
  - PK prior to vadadustat or epoetin alfa dosing (see [Section 9.2.2.1](#), PK/PD Sampling for Subjects Randomized to Vadadustat and [Section 9.2.2.2](#), PK Sampling for Subjects Randomized to Epoetin Alfa) and prior to the dialysis session
- Review of medical history for new conditions since SV2
- Review of medication use since SV2
- Study drug assessments and procedures:
  - Subject will take/receive their first dose of study drug at the study site during Baseline/Day 1

- For subjects in the vadadustat treatment arm only:
  - Initiate vadadustat dosing
  - Vadadustat drug dispensation
  - Review vadadustat dosing instructions
- Epoetin alfa dosing will continue for the subjects in the epoetin alfa arm
- Iron supplementation as needed to maintain ferritin  $\geq 100$  ng/mL or TSAT  $\geq 20\%$  (per local product label; see [Section 8.4.8, Iron Supplementation](#))

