### 9.3.3 Visit 2 to Visit 13 (Weeks 1 to 20)

At the Baseline/Day 1, Visit 7 and Visit 9, subjects in the vadadustat treatment arm will be reminded and instructed to hold their vadadustat dose on the day of Visit 2, Visit 8, and if applicable Visit 10, respectively, as blood sample for PK analysis will be collected on the day of Visit 2, Visit 8, and Visit 10 prior to vadadustat administration at the study site.

The following activities/procedures will be performed at Visit 2 to Visit 13, unless noted otherwise:

- Abbreviated, symptom-directed physical examination, at the discretion of the Investigator, as clinically indicated
- Vital signs including temperature, HR, BP, RR and SO2 (assessed in seated position after 5 minutes of rest and prior to blood draws). Dry weight will be collected at Visit 9 only.
  - A status check (BP, vital signs, and review of current health status) will be performed during weeks with no scheduled study visit.
- Dialysis adequacy, as available from local information (Visit 9 only)
- SF-36 and PGI-S assessments (Visit 9 only)
- Safety assessments:
  - AE review
  - RBC transfusions and ESA rescue
  - Therapeutic phlebotomy
- Laboratory procedures (if blood samples are collected on a day of dialysis, blood draws will be done prior to dialysis, if applicable):
  - CBC
  - Reticulocyte count (Visit 2, 4, 6, 8, 9, 10 and 12 only)
  - CRP (Visit 9 only)
  - Serum chemistry (Visit 9 only)
  - LFTs (Visit 4, 6, 9 and 12 only)
  - Iron indices (Visit 4, 6, 9 and 12 only)
  - Biomarkers (VEGF and Hepcidin, Visit 9 only)
  - Vadadustat PK/PD sampling (Visit 2, 8 and 10 only) for details, see [Section 9.2.2.1, PK/PD Sampling for Subjects Randomized to Vadadustat](#) and [Section 9.2.2.3, PK/PD Sampling](#)

- Epoetin alfa PK sampling (Visit 2 only) for details, see [Section 9.2.2.2](#), PK Sampling for Subjects Randomized to Epoetin Alfa and [Section 9.2.2.3](#), PK/PD Sampling)
- Medication assessments and procedures:
  - Review of concomitant medications
  - Subjects in epoetin alfa treatment arm will continue to receive epoetin alfa
  - For subjects in the vadadustat treatment arm only:
    - Visit registration in IWRS (for bottle dispensing only)
    - Vadadustat drug dispensation (scheduled Visits 4, 6, 9 and 12)
    - Review vadadustat dosing instructions
    - Review of vadadustat dosing compliance
    - Vadadustat reconciliation

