Dosage and Regimens	
The aim is to achieve and maintain Hb levels within the target range of 10.0 to 11.0 g/dL, inclusive, while targeting the middle of the range and minimizing excursions outside the target range.
 
Dosing will be initiated at Baseline/Day 1 and the first dose of vadadustat will be administered at the study site after other Baseline/Day 1 procedures have been completed.
 
Thereafter, vadadustat will be taken once daily on an outpatient basis. Subjects may take vadadustat with or without food and will be instructed to swallow the tablet(s) whole. Subjects will be instructed to take vadadustat at roughly the same time each day.
 
Epoetin alfa dose will be administered intravenously at the hemodialysis clinic, based on the subject's central laboratory Hb value and the approved epoetin alfa US PI for adult patients with CKD on dialysis.
 
Note: For all subjects, no epoetin alfa will be administered after SV2 after the subject has met all eligibility criteria and before Baseline/Day 1, for a minimum duration of 5 days in the Main study and 2 days in the ESA hyporesponder parallel study.
 
Main Study: Subjects will be randomized to either a vadadustat treatment arm or epoetin alfa treatment arm. Randomization will be stratified by mean weekly epoetin alfa dose calculated over a period of 8 weeks prior to SV2:
 

• Low epoetin alfa dose group (<math>\leq</math>90 U/kg/week) or

• High epoetin alfa dose group (<math>></math>90 to <math><</math>300 U/kg/week)

 
In the low epoetin alfa dose group, subjects will be randomized in a 3:3:2 ratio to receive either an initial vadadustat daily dose of 450 mg (3 tablets) or 300 mg (2 tablets), or epoetin alfa.
 
In the high epoetin alfa dose group, subjects will be randomized in a 3:3:3:2 ratio to receive either an initial vadadustat daily dose of 600 mg (4 tablets), 450 mg (3 tablets) or 300 mg (2 tablets), or epoetin alfa.
 
ESA Hyporesponder Parallel Study Subjects will be randomized in a 1:1 ratio to receive either an initial vadadustat daily dose of 600 mg (4 tablets) or epoetin alfa.

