PK/PD Sampling - vadadustat arm	
Blood for measurement of vadadustat, metabolites and EPO level in the vadadustat arm, in both the Main study and ESA hyporesponder parallel study, will be collected as outlined below (see Appendix B). Preferably, PK/PD samples are to be taken on the day of hemodialysis after the first short interdialytic interval (e.g., at the second session of the week).
 
At Baseline/Day 1, PK/PD samples will be collected prior to dialysis and administration of vadadustat.
 
At Week 1 (after at least a full week of vadadustat treatment), vadadustat will be administered between 15 minutes to one hour prior to the start of dialysis. Blood samples will be collected as follows:
 

• 15 minutes pre-dose, and 2 hours <math>\pm</math> 15 minutes, 3.5 hours <math>\pm</math> 15 minutes, and 5 hours <math>\pm</math> 30 minutes post-dose

• From subjects enrolled at a subset of study sites only, additional samples will be collected at 7 hours <math>\pm</math> 30 minutes and 10.5 hours <math>\pm</math> 1.5 hours post-dose

 
On the following non-dialysis day, blood samples will be collected as follows:
 

• 15 minutes pre-dose, and 2 hours <math>\pm</math> 15 minutes, 3.5 hours <math>\pm</math> 15 minutes, and 5 hours <math>\pm</math> 30 minutes post-dose

• From subjects enrolled at a subset of study sites only, additional samples will be collected at 7 hours <math>\pm</math> 30 minutes post-dose

 
At Week 11, vadadustat will be administered between 15 minutes to one hour prior to the start of dialysis. Blood samples will be collected as follows:
 

• 15 minutes pre-dose, and 2 hours <math>\pm</math> 15 minutes, 3.5 hours <math>\pm</math> 15 minutes, and 5 hours <math>\pm</math> 30 minutes post-dose

• From subjects enrolled at a subset of study sites only, additional samples will be collected at 7 hours <math>\pm</math> 30 minutes and 10.5 hours <math>\pm</math> 1.5 hours post-dose

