#### **4.2 Summary of Clinical Experience**

*Please see the vadadustat Investigator Brochure for additional discussion and information for the following section.*

The efficacy, safety, tolerability, pharmacokinetic (PK), and pharmacodynamic (PD) profiles of vadadustat have been characterized in 10 completed Phase 1 studies in healthy volunteers including 1 ethno-bridging study in Caucasian and Japanese subjects, 1 completed Phase 1 study in subjects undergoing chronic hemodialysis, 3 completed Phase 2a studies in non-dialysis dependent CKD (NDD-CKD) subjects, 1 completed Phase 2b study in NDD-CKD subjects, and 1 completed Phase 2 study in DD-CKD subjects. The United States (US) Phase 2a studies evaluated Stages 3, 4, and 5 CKD (not on dialysis) subjects in a single-dose PK study, a multi-dose, 28-day, open-label, dose escalation pilot study, and a randomized, double-blind, placebo-controlled study with 5 different dose groups dosed for 42 days. The US Phase 2b, randomized, double-blind, placebo-controlled study evaluated Stages 3, 4, and 5 CKD (pre-dialysis) dosed for 20 weeks. The Japanese Phase 2, randomized, double-blind, placebo-controlled study evaluated Stages 3, 4, and 5 CKD (pre-dialysis) dosed for 16 weeks. The US Phase 2 open-label study evaluated DD-CKD subjects on chronic hemodialysis dosed for 16 weeks. The Japanese Phase 2, randomized, double-blind, placebo-controlled study evaluated DD-CKD subjects on chronic hemodialysis dosed for 16 weeks. In the studies completed to date, a total of 630 subjects have received vadadustat, including 200 healthy volunteers and 430 subjects with CKD.

Vadadustat has shown dose-dependent increases in EPO concentrations in Phase 1 and Phase 2a studies. The changes in EPO have been accompanied by an increase in reticulocytes and Hb as well as dose responsive increases in total iron binding capacity (TIBC) and decreases in hepcidin and ferritin. Overall, the safety profile for vadadustat has been acceptable and has supported further development. Vadadustat has demonstrated consistent bioavailability with area under concentration-time curve (AUC) and  $C_{max}$  in Phase 1 and Phase 2 studies covering the dose range

of 80 mg to 1200 mg after single administration and 500 to 900 mg after repeated daily administration for 10 days. The plasma half-life of vadadustat was about 4 to 6 hours, 7 to 8 hours, and 9 to 10 hours in healthy subjects, NDD-CKD patients, and DD-CKD patients, respectively.

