#### 8.4.7 Late or Missed Doses

Subjects on vadadustat will be instructed to take the study drug at approximately the same time each day. If a dose is forgotten, subjects will be instructed to take the dose as soon as they remember during the same day.

- Daily dosing regimen: If a forgotten dose is not remembered on the same day, the subject will skip the dose and resume the normal dosing schedule the following day.
- TIW dosing regimen: If a forgotten dose is not remembered on the same day, the subject will take the dose on the following day (a non-dialysis day). If a forgotten dose is not remembered on the same day or the following day of a long interdialytic gap, the subject will take the dose on the subsequent day (the second non-dialysis day). Thereafter, the subject should resume the normal dosing schedule.
- Subjects will not double-up on missed doses.

Epoetin alfa dose (including handling of late or missed dose) will be administered at the site and titrated based on the subject's central laboratory Hb value and the approved epoetin alfa US PI for adult patients with CKD on dialysis.

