## **8.4.11 Treatment Compliance**

Throughout the study, subjects in the vadadustat arm will be guided regarding dosing compliance using an eDiary. The focus of the vadadustat eDiary is to guide subjects to remind them of the dose, instruct them to hold their dose for the PK/PD sample dates and guide them if they have transitioned from daily dosing to TIW dosing. Subjects will also be questioned at study visits on whether they have questions or have experienced any problems related to the dosing of vadadustat. Subject compliance with eDiary data entry will be routinely monitored to identify potential issues that may impact or prevent data entry. The Investigator will also maintain drug accountability logs itemizing all study drugs dispensed to and returned from each subject during

the study. Treatment compliance will be determined from these logs, subject questioning, and the study drug Case Report Form (CRF)

For epoetin alfa, the dose that is administered is required to be entered in the electronic data capture (EDC) system, and the EDC system will be used to determine dosing compliance.

Subjects who miss doses will be counseled on the importance of compliance.

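### The Week 1 and Week 11 PK doses are timed to dialysis, but nothing shown times the home dose before them, so the interval before the PK dose can be far from 24 h

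*Protocol*

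**What the plan says.** The document holds two protocol versions. The earlier one is complete through its appendices; the later one breaks off at the start of Section 9.

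- **PK-day dose.** The Synopsis (PK/PD Sampling, vadadustat arm) states for Weeks 1 and 11 that "vadadustat will be administered between 15 minutes to one hour prior to the start of dialysis". Section 9.2.2.1 of the earlier version says the same. Week 1 also requires a full week of prior treatment, which fixes the number of earlier doses but not the hour of the last one.
- **Home doses.** Synopsis, Dosage and Regimens: "Subjects will be instructed to take vadadustat at roughly the same time each day". Section 8.4.7: "Subjects on vadadustat will be instructed to take the study drug at approximately the same time each day". Neither names a clock time or refers to the dialysis shift.
- **Instructions for PK visits.** Under Section 8.4.11 the eDiary is to "instruct them to hold their dose for the PK/PD sample dates". Section 9.3.3 of the earlier version has subjects "reminded and instructed to hold their vadadustat dose on the day of Visit 2, Visit 8, and if applicable Visit 10". Both concern the PK-day tablet only.
- **Recording.** Section 9.2.2.3 and Appendix A, footnote [w] (earlier version), require the previous dose time, the PK dose time and the dialysis start and stop times to be recorded.
- **Use of the data.** The Synopsis (Statistical Considerations) plans descriptive summaries of PK parameters and mean and individual concentration–time plots, plus a population PK analysis reported separately.
- **Half-life.** Section 4.2 gives "and 9 to 10 hours in healthy subjects, NDD-CKD patients, and DD-CKD patients, respectively".

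**The concern.** Two instructions meet on the PK day: keep a constant hour at home, and take the PK dose just before dialysis. They agree only for subjects whose usual hour is just before dialysis. Someone who keeps the timing of the supervised Day 1 dose has about 24 h between doses and no problem. Someone who doses in the evening and dialyses in the morning has a short interval because both instructions were followed. Section 9.3.2 of the earlier version foresees a case where "dialysis treatment is scheduled for early morning of Baseline/Day 1", so this is not far-fetched. A morning doser with later dialysis has a long interval.

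With a 9 to 10 h half-life, carry-over from the last dose is not negligible. It raises or lowers the observed pre-dose sample and, to a lesser degree, observed AUClast and the mean profiles, which serve the secondary PK/PD objective.

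Week 1 has a further consequence, because it samples a dialysis day and the following non-dialysis day. If the second dose comes 24 h after the first, the irregular carry-over falls mainly on the dialysis day and can look like an effect of dialysis.

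**Working it through.** The plan states no figure to reproduce; this is a check of size.

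**Inputs.** Half-life 9, 9.5 and 10 h (Section 4.2). Planned samples at pre-dose, 2, 3.5 and 5 h. About 15 subjects per vadadustat arm (Synopsis schematic). *Assumed*, because the documents give none: one compartment, linear kinetics, absorption rate ka of 0.5, 1, 2 or 1000 per hour (the last near-instant), and a range of gaps g between the last home dose and the PK dose.

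**Model.** Each dose contributes C(t) = ka/(ka−k)·[exp(−kt) − exp(−ka·t)], with k = ln 2/half-life. The PK dose is at time 0 and 60 earlier doses are at −g, −g−24, and so on. The reference has g = 24 h.

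**By hand, near-instant absorption, half-life 9 h, g = 12 h.**
- Fraction left after 24 h: 2^(−24/9) = 0.1575. Reference pre-dose level, in units of one dose: 0.1575/(1 − 0.1575) = 0.187.
- Pre-dose ratio: 2^((24−12)/9) = 2.52, so the level is 0.187 × 2.52 = 0.471. With half-life 10 h the ratio is 2^(12/10) = 2.30.
- AUC0–5h ratio: (1 + 0.471)/(1 + 0.187) = 1.24.

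**Full grid, ratio to a 24 h gap (range over 12 combinations).**

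| Gap | Pre-dose | AUC0–5h, integrated | AUC0–5h, trapezoid on planned samples |
|---|---|---|---|
| 12 h | 2.29–2.52 | 1.24–1.38 | 1.30–1.40 |
| 16 h | 1.74–1.85 | 1.13–1.22 | 1.17–1.23 |
| 20 h | 1.32–1.36 | 1.06–1.09 | 1.07–1.10 |
| 28 h | 0.73–0.76 | 0.93–0.96 | 0.93–0.95 |
| 32 h | 0.54–0.57 | 0.88–0.93 | 0.87–0.91 |

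Between 20 and 28 h the AUC0–5h error stays under 10%.

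**Arm means.** If a share p has gap g and the rest 24 h, with equal dose and kinetics, the ratio of means is 1 + p·(ratio − 1).
- 3 of 15 at 12 h: pre-dose 1 + 0.2 × 1.287 to 1 + 0.2 × 1.520, i.e. +26 to +30%; AUC0–5h 1 + 0.2 × 0.239 to 1 + 0.2 × 0.380, i.e. +5 to +8%.
- 5 of 15 at 12 h: +43 to +51% and +8 to +13%.
- Half at 12 h: +64 to +76% and +12 to +19%.
- 3 of 15 at 16 h: +15 to +17% and +3 to +4%.
- 3 of 15 at 12 h and 3 of 15 at 32 h: +17 to +21% and +3 to +5%. Long gaps offset short ones only in part.

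The arm-mean AUC0–5h shift stays under 10% while no more than a quarter of the arm is at 12 h.

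**Week 1 two-day contrast.** With g = 12 h, the non-dialysis-day dose 24 h later and no true dialysis effect, the dialysis-day AUC0–5h is 1.19 to 1.30 times, and the pre-dose level 1.84 to 2.03 times, the next-day value in the same subject.

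**Effect of aligning doses, home gap otherwise 12 h.** One aligned dose leaves pre-dose at 1.24 to 1.25 and AUC0–5h at 1.04 to 1.07. Two leave 1.04 to 1.05 and about 1.01.

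**Week 13.** On three-times-weekly dosing, 48 h after a dose 2^(−48/9) = 2.5% to 2^(−48/10) = 3.6% of it remains; at 36 h it is 6 to 8%. Alignment matters little there.

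**The case against.** The protocol never promises a controlled 24 h interval. It asks for a regular hour, gives the first dose before dialysis, holds the PK-day dose and records the actual times, which is a usual approach when population PK is the main tool. The largest effect is on the pre-dose level, and no trough parameter is named in the PK list. With most sites sampling only to 5 h against a 9 to 10 h half-life, clearance, volume, half-life and AUCinf can hardly come from raw profiles and will lean on the model, which uses actual times. By Week 11 doses have been titrated individually between 150 and 900 mg, which may move arm means more than timing does. Where sampling runs to 10.5 h, the AUC error at a 12 h gap is +24 to +31% instead of +24 to +38%. The later version's Section 9, the eDiary text and the site instructions are not shown.

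Most of this stands and limits the weight of the point. It does not remove it. Observed parameters and mean profiles are still to be reported. Recording the interval allows a profile to be flagged or dropped, which is costly with about 15 per arm, but does not restore a 24 h interval. When a tablet is taken is a matter for the protocol. Titration does not change the within-subject ratios under linear kinetics, and does not explain away the Week 1 contrast.

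**Conclusion.** The point holds as an optional improvement. No text shown times the dose before the Week 1 or Week 11 PK dose, so subjects who follow every instruction can enter the observed summaries with an interval well away from 24 h. At a 12 h gap the affected subject's pre-dose level is 2.3 to 2.5 times, and AUC0–5h 24 to 38% above, the 24 h value; within 20 to 28 h the AUC error is below 10%.

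These sizes rest on the stated half-life, a one-compartment linear model and assumed gaps. The documents give no home dosing times or dialysis shifts, so the share affected cannot be estimated. The damage is confined to observed PK summaries for a secondary, descriptive objective in an exploratory study. The population PK model and the hemoglobin endpoint are not affected. The absence in Section 9 is established from the earlier version only; the later version's Synopsis and Section 8 contain no aligning text either.

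**What to change.** Unless the later version's Section 9 already covers it, add to Sections 9.2.2.1 and 9.3.3, and to the eDiary prompt that already covers PK days:

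> On the day before (preferably the two days before) the Week 1 and Week 11 PK visits, take vadadustat at the clock time of the planned pre-dialysis dose. Take the Week 1 non-dialysis-day dose about 24 h after the dialysis-day dose.

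Week 13 needs no change. Any rule for flagging off-interval profiles can be left to the analysis plan.

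The cost is one or two sentences and an eDiary text change, with no added visit, sample or dose. Some subjects shift their home dosing hour for a day or two and may have to re-space phosphate binders. The irregular interval is moved one or two days earlier, not abolished, and the aligned doses are unsupervised.

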## 11 DATA ANALYSIS

Data collected throughout the study will be summarized using descriptive statistics and listed in the by-subject listings. Continuous variables will be summarized using number of subjects with mean, standard deviation (SD), median, minimum, and maximum. For categorical variables, the number and percentage of subjects in each category will be tabulated. Summaries will be provided by treatment group within appropriate analysis populations (as defined in Section 11.2, Study Analysis Populations) and by time point/time period, as appropriate.

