### **11.6 Efficacy Analyses**

The primary efficacy endpoint as well as all other secondary endpoints will be summarized using descriptive statistics (means or proportions) by treatment groups and in total, as well as by study visit and/or analysis period as appropriate. Mean values of Hb as well as selected other efficacy parameters will be plotted across study visits/periods by treatment group.

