## 2 PROTOCOL SYNOPSIS

Study Title	Phase 2, Randomized, Open-Label, Active-Controlled, Efficacy, Safety, Pharmacokinetics, and Pharmacodynamics Study of Oral Vadarustat for the Treatment of Anemia in Hemodialysis Subjects Converting from Epoetin Alfa
Protocol Number	AKB-6548-CI-0025
Study Phase	Phase 2
Investigational Product	Vadarustat; 150 mg tablets
Reference Medicinal Product	Epoetin alfa solution for intravenous (IV) injection in multi-dose vials or in single-dose vials
Study Population	The Main study population will consist of adult subjects receiving chronic, outpatient in-center hemodialysis three times weekly (TIW), with 2 screening hemoglobin (Hb) values between 8.5 and 11.0 g/dL (inclusive) and on maintenance treatment with epoetin alfa <300 U/kg/week. The erythropoiesis stimulating agent (ESA) hyporesponder parallel study will consist of adult subjects receiving chronic, outpatient in-center hemodialysis TIW, with 2 screening Hb values between 8.0 and 10.0 g/dL (inclusive) and on maintenance treatment with epoetin alfa ≥300 U/kg/week.
Study Sites	Approximately 40 study sites in the United States
Planned Number of Subjects	Approximately 125 subjects • Main study: ~95 subjects • ESA hyporesponder parallel study: ~30 subjects
Primary Objective	To assess the efficacy and safety of daily dosing of vadarustat compared to epoetin alfa for 12 weeks in hemodialysis subjects
Secondary Objectives	

• To assess the efficacy and safety of TIW dosing of vadarustat in selected hemodialysis subjects who have been successfully managed with daily dosing of vadarustat through Week 12

• To evaluate the pharmacokinetics (PK)/pharmacodynamics (PD) of daily and TIW dosing of vadarustat in hemodialysis subjects compared to epoetin alfa

• To assess the efficacy and safety of several dosing strategies of vadarustat compared to epoetin alfa during a 20-week Treatment Period in hemodialysis subjects

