
Study Termination/ Individual Study Site Termination
	
The Sponsor may terminate this study prematurely, either in its entirety or at any study site, for reasonable cause provided that written notice is submitted in advance of the intended termination. Advanced notice is not required if the study is stopped due to safety concerns. If the Sponsor terminates the study for safety reasons, the Sponsor will immediately notify the Investigator and subsequently provide written instructions for study termination. If the study has been suspended or terminated, prompt notification will be given to Investigators, IRBs, and regulatory authorities in accordance with regulatory requirements.

Statistical Considerations
	
Efficacy and safety endpoint analysis will be descriptive in nature. Continuous variables will be summarized using number of subjects with mean, standard deviation (SD), median, minimum and maximum. For categorical variables, the number and percentage of subjects in each category will be tabulated.

	PK and PD parameters will be summarized using descriptive statistics: number of subjects, mean, median, SD, minimum, maximum, and coefficient of variation, geometric mean and geometric mean SD. Mean and individual plasma concentration-time profiles will be presented graphically in both linear scale and log-linear scale. The ESA hyporesponder parallel study will be analyzed separately from the main study.
PK Analysis	A population PK analysis will be conducted to describe vadadustat PK and determine the covariates that impact the PK profile (i.e., demographics, laboratory values, concomitant iron, dosing relative to dialysis, etc). PK analysis will be reported separately.
PD Analysis	An exposure-response analysis of vadadustat, EPO and other PD measures will be conducted as deemed appropriate. PD analysis will be reported separately.

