Sample Size Estimation	Approximately 95 subjects are planned for enrollment in the Main study with 40 and 55 subjects randomized to the low epoetin alfa dose group and the high epoetin alfa dose group respectively. Approximately 30 subjects are planned for enrollment in the ESA hyporesponder parallel study. Sample size reflects the exploratory nature of this study.  Enrollment may be increased by up to 20 additional subjects in the Main study, and by up to 30 additional subjects in the ESA hyporesponder parallel study to ensure adequate data is captured for the primary, PK/PD, and safety endpoints.
Safety Monitoring	This is an open label study allowing the study team full access to safety data which will be reviewed on a regular basis, throughout the course of the study. Safety monitoring will be performed as described in the Medical Monitor Plan.

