## 5 STUDY OBJECTIVES AND ENDPOINTS

### 5.1 Primary Objective

To assess the efficacy and safety of daily dosing of vadadustat compared to epoetin alfa for 12 weeks in hemodialysis subjects.

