### 5.3 Efficacy Endpoints

#### 5.3.1 Primary Endpoints

The primary endpoint will be the mean change in Hb between Baseline (average pretreatment Hb) and the primary evaluation period (average Hb from Weeks 10 to 12).

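### The primary objective compares vadadustat with epoetin alfa, but the protocol as shown fixes per-arm summaries of raw Hb change and names no between-arm difference, interval or adjustment

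*Protocol*

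**What the plan says.** The protocol's title describes the trial as "Phase 2, Randomized, Open-Label, Active-Controlled, Efficacy, Safety" and so on. Section 5.1 gives the primary objective: "To assess the efficacy and safety of daily dosing of vadadustat compared to epoetin alfa for 12 weeks in hemodialysis subjects". The primary endpoint (Section 5.3.1) is each subject's Hb change from the pretreatment average to the average over Weeks 10 to 12.

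The analysis is stated in three places:

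- **Synopsis, Statistical Considerations:** "Efficacy and safety endpoint analysis will be descriptive in nature", followed by "Continuous variables will be summarized using number of subjects with mean, standard deviation (SD), median, minimum and maximum".
- **Section 11:** "Continuous variables will be summarized using number of subjects with mean, standard deviation (SD), median, minimum, and maximum".
- **Section 11.6:** the primary and secondary endpoints are "summarized using descriptive statistics (means or proportions) by treatment groups and in total".

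On sample size the protocol says "Sample size reflects the exploratory nature of this study". Section 11.3 refers to the statistical analysis plan for the detailed definition of analysis populations, and none of the analysis text shown refers to it for the efficacy method.

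**The concern.** The objective asks how vadadustat compares with epoetin alfa. The listed outputs describe each arm separately, so an analysis that follows the text literally contains no estimate of the comparison.

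The choice of endpoint adds to this. Main-study screening Hb may lie anywhere from 8.5 to 11.0 g/dL, and every subject is titrated to 10.0 to 11.0. To reach the target range, a subject entering at 8.5 must rise by at least 1.5 g/dL, while one entering at 11.0 need not rise at all. Raw change therefore depends on where a subject starts, and with 10 to 15 subjects per arm, mean baselines will differ by chance.

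The epoetin-dose strata are also mixed unequally once doses are pooled. Section 4.2 reports that in the previous hemodialysis study a higher prior epoetin dose went with a fall in Hb, so stratum is a plausible prognostic factor.

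The study is meant to help characterize the best vadadustat regimen. Readers will compare the arm means whether or not the plan does it for them, and they would do so without the adjusted estimate that data already collected could supply.

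**Working it through.** **Planned numbers (reproduced).** Inputs are the stratum sizes in Section 11.1 and the ratios in Section 8.4.1.

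- Low stratum, 40 at 3:3:2: 15 / 15 / 10.
- High stratum, 55 at 3:3:3:2: 15 / 15 / 15 / 10.
- Hyporesponder study, 30 at 1:1: 15 / 15.
- Totals: 40 + 55 = 95; 95 + 30 = 125.

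These agree with the study schematic. No power, alpha, effect size or SD is stated, so there is no power calculation to reproduce.

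**Stratum mix when doses are pooled.** High-stratum share: vadadustat 45/75 = 60%; epoetin 10/20 = 50%. If the strata differed by an assumed 0.5 g/dL in mean change, the unadjusted pooled contrast would shift by (0.60 − 0.50) × 0.5 = 0.05 g/dL. The 600 mg Main arm lies wholly in the high stratum, so against pooled epoetin it would shift by (1.00 − 0.50) × 0.5 = 0.25 g/dL.

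**Precision of an unadjusted difference.** Half-width = t(0.975, n1+n2−2) × SD × √(1/n1 + 1/n2). The SD of the change is assumed, since the documents give none.

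| Contrast | SD 0.8 | SD 1.0 | SD 1.2 |
|---|---|---|---|
| One dose arm vs epoetin, 15 vs 10 | 0.68 | 0.84 | 1.01 |
| Main study pooled, 75 vs 20 | 0.40 | 0.50 | 0.60 |
| Hyporesponder, 15 vs 15 | 0.60 | 0.75 | 0.90 |

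Example, 15 vs 10 at SD 1.0: 2.069 × 1.0 × 0.408 = 0.84 g/dL.

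**How much baseline imbalance carries over.** Let sb and sf be the baseline and follow-up SDs and r their correlation. The regression slope of follow-up on baseline is b = r × sf/sb. With no treatment effect, a baseline difference d between arms produces an expected change-score difference of −(1 − b) × d, so a share 1 − b carries through.

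**Variance of ANCOVA relative to change scores.** Ratio = sf²(1 − r²) / (sb² + sf² − 2·r·sb·sf).

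| Assumed inputs | Share carried, 1 − b | Variance ratio | Cut |
|---|---|---|---|
| sb = sf, r = 0.2 | 80% | 0.96/1.60 = 0.60 | 40% |
| sb = sf, r = 0.4 | 60% | 0.84/1.20 = 0.70 | 30% |
| sb 0.6, sf 0.9, r = 0.2 | 70% | 0.778/0.954 = 0.82 | 18% |
| sb 0.6, sf 0.9, r = 0.4 | 40% | 0.680/0.738 = 0.92 | 8% |

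With baseline SD 0.6, the standard error of the baseline difference for 15 vs 10 is 0.6 × 0.408 ≈ 0.24 g/dL. A one-standard-error imbalance therefore moves the change-score contrast by about 0.10 to 0.20 g/dL (40 to 80% of 0.24).

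In interval width the gain is smaller: √0.60 = 0.77 and √0.92 = 0.96, a narrowing of about 4 to 23%. The 0.84 g/dL half-width becomes about 0.65 to 0.81.

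**The case against.** The descriptive stance is deliberate, disclosed and usual for an exploratory Phase 2 study. The objective claims neither superiority nor non-inferiority. Calling an analysis descriptive rules out confirmatory testing but does not forbid a difference with an interval, and models and covariates normally belong in the SAP. All arms are titrated to one target, which pushes Hb differences toward zero.

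Much of this stands: tests and power are not needed. It does not remove the point, because the protocol does not leave the method open. It sets the type of analysis and lists the statistics, and that list does not answer the stated objective.

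Several stronger readings are tempting but not supported:

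- **That no uncertainty is reported.** Per-arm n, mean and SD give a crude difference and interval. Only the adjusted contrast is out of reach.
- **That no comparison will ever be produced.** The SAP is not shown, and Section 11 of the later protocol version lies outside the part available. The later synopsis repeats the descriptive wording, but the statement holds only for the protocol as shown.
- **That baseline imbalance passes wholly into the result, or that change is mostly determined by baseline.** The share is about 40 to 80% under the assumptions above, and the documents contain no data to fix it.
- **That every interval is at least as wide as the protocol's 0.5 g/dL threshold.** The pooled half-width is 0.40 at SD 0.8. The 0.5 g/dL figure is a within-subject response criterion and dose-adjustment trigger, not a between-arm margin.
- **That adjustment would make single-dose contrasts precise.** At 15 vs 10 they stay wide.

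**Conclusion.** The point holds as a mismatch between a comparative primary objective and an analysis fixed, in the protocol as shown, as per-arm summaries. Its size is moderate. Adjustment guards against a contrast moved by roughly 0.10 to 0.20 g/dL for a typical chance baseline imbalance (15 vs 10, baseline SD 0.6). It also cuts the variance of the change-score contrast by 8 to 40%. Stating the interval would show that one dose arm against epoetin is known only to within about 0.68 to 1.01 g/dL, and the pooled comparison to within 0.40 to 0.60.

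These figures assume a change SD of 0.8 to 1.2 g/dL, a baseline to follow-up correlation of 0.2 to 0.4, and either equal SDs or 0.6 at baseline with 0.9 at follow-up. The allocation figures are the protocol's own. The change should be made, but the trial's exploratory purpose does not depend on it.

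**What to change.** Keep the analysis free of hypothesis tests. In the synopsis (Statistical Considerations) and Section 11.6, add two statements:

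1. The primary endpoint is also reported as the vadadustat minus epoetin difference in Weeks 10 to 12 Hb, from ANCOVA with baseline Hb as covariate, plus epoetin-dose stratum when strata are pooled. It is given with a 95% CI, for each starting dose within stratum and overall in the Main study, and separately in the hyporesponder study. It is interpreted as estimation only.
2. The key secondary proportion within the target range at Weeks 10 to 12 is also reported as a between-arm difference with a 95% CI.

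The cost is about two sentences and one extra table column. Baseline Hb and the stratum are already collected, so no further subjects, visits or data are needed. If the sponsor does not want a between-arm estimate, the consistent alternative is to reword the primary objective as descriptive.
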